### 14.2 Data Analysis

Hormone concentrations and tissue PSA, TMPRSS2, FKBP5, EZH2, H3K27, and UBE2C measured by qPCR will be summarized as means and standard errors, possibly after data transformation. Differences between genotypes within and between tissue types will be analyzed using linear or non-linear models.

Pearson or Spearman rank correlations will be used to assess associations between the concentrations of the different hormones and molecular markers. All tests of statistical significance will be two-sided.

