## PROTOCOL SUMMARY

Protocol Number/Title	
CASE5815
 
The Association Between HSD3B1 Genotype and Steroid Metabolism in Normal and Prostate Cancer Tissue of Men with Intermediate and High-risk Prostate Cancer Undergoing Radical Prostatectomy after a short-term treatment with Apalutamide and leuprolide acetate.

Study Phase	Phase II Study
Brief Background/Rationale	
As homozygosity for HSD3B1(1245C) SNP can impact response and mediate resistance to androgen deprivation therapy (ADT), evaluating the effect of such genotype variation on the level of steroid metabolites and the intratumoral DHT concentration in benign and tumor tissue of men receiving a short course of Apalutamide and leuprolide acetate prior to undergo RP is of significant interest. We hypothesize that patients with homozygous HSD3B1 (1245C) inheritance that leads to a gain of function in <math>\beta</math>HSD1, will have a sustained androgen synthesis from extragonadal precursor steroids and higher concentrations of DHT compared to patients with wild-type HSD3B1 (1245A) inheritance in the context of testosterone suppression. In addition, it is expected that heterozygous HSD3B1 (1245C) patients will have intermediate levels of DHT. We also hypothesize that treatment with Apalutamide will reverse the effects of elevated DHT on AR signaling in benign and malignant prostate tissue. For example, although DHT concentrations will be higher in the HSD3B1 (1245C) groups, PSA expression will likely be similar among all groups. We anticipate that these studies will serve as the first step in identifying patients with localized and locally advanced prostate cancer who will benefit from upfront treatment with Apalutamide in addition to medical castration prior to undergo local definitive therapy with surgery.

Primary Objective	
Primary Endpoint
 
DHT concentration in benign prostate tissue after neo-adjuvant leuprolide and Apalutamide based on genotype status

Secondary Objective(s)	
Secondary Endpoint(s)
 
 
1. Other androgens (testosterone (T), dehydroepiandrosterone (DHEA), androstenediol, 5<math>\alpha</math>-androstenedione (5<math>\alpha</math>-dione), androstenedione (AD),
 

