**11 STUDY CALENDAR**

**12 MEASUREMENT OF EFFECT**

**13 RECORDS TO BE KEPT/REGULATORY CONSIDERATIONS**

13.1 Data reporting

13.2 Regulatory considerations

**14 BIOSTATISTICAL CONSIDERATIONS**

**15 REFERENCES**

# 1 Introduction

## 1.1 Prostate Adenocarcinoma

Prostate cancer represents 14.0% of all new cancer cases in the U.S. It is the second most common cause of cancer death in American males and the leading cause of cancer death in males over 85. In 2015, it is estimated that there will be 220,800 new cases of prostate cancer and an estimated 27,540 people will die of this disease. Androgen deprivation therapy (ADT), with either medical or surgical castration, is a critical and the most effective component of therapy for patients with metastatic or high-risk localized prostate cancer. Normally, serum testosterone (T) is irreversibly converted to DHT in the prostate by steroid 5 $\alpha$ -reductase (SRD5A). Dihydrotestosterone (DHT) is the chief endogenous agonist for the androgen receptor (AR) and binds and activates AR with 10-fold higher potency than T. ADT lowers serum T concentrations to less than 1.7 nmol/l and generates an initial tumor response in about 90% of the patients. However, nearly all patients will eventually progress to a “castration-resistant” state.

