### 1.4 Androgen Metabolism

The major sites of chemical modification on the steroid backbone for DHT synthesis are carbons 3, 5 and 17, which are modified in 3 enzymatic steps for the conversion of DHEA to DHT (Figure 1). DHEA is a 3 $\beta$ -hydroxy,  $\Delta^5$  steroid (double bond between carbons 5 and 6) and is enzymatically converted in CRPC tissues to  $\Delta^4$ -androstenedione (AD) by 3 $\beta$ HSD. 3 $\beta$ HSD1 and 3 $\beta$ HSD2 are the two human isoenzymes that possess this enzymatic activity. 3 $\beta$ HSD1 is thought to be the peripherally expressed isoenzyme and 3 $\beta$ HSD2 the isoenzyme in steroidogenic organs. However, both are detected in CRPC. We have previously shown that 3 $\beta$ HSD enzymatic activity is absolutely required for the synthesis of T and/or DHT, downstream AR nuclear translocation, expression of AR-responsive genes and CRPC growth. It was generally thought that AD undergoes conversion to T, which is then converted to DHT by SRD5A. However, we have recently shown that an alternative pathway is dominant, not only in cell line models but also in freshly collected tumors from patients with CRPC. In this pathway, SRD5A converts AD to 5 $\alpha$ -androstenedione (5 $\alpha$ -dione), which is then converted to DHT. Furthermore, we have shown that only one of two SRD5A isoenzymes, SRD5A1, is specifically required in this pathway. We have also demonstrated that a pitfall of pharmacologically blocking SRD5A with dutasteride is that AD is instead

diverted to increased synthesis of T, compensating in part for depletion of the more potent DHT, resulting in modest clinical activity of SRD5A inhibition against CRPC.

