## 1.7 Study Rationale

As homozygosity for *HSD3B1*(1245C) SNP can impact response and mediate resistance to ADT, evaluating the effect of such genotype variation on the level of steroid metabolites and the intratumoral DHT concentration in benign and tumor tissue of men receiving a short course of Apalutamide and leuprolide prior to undergo RP is of interest. We hypothesize that patients with homozygous *HSD3B1* (1245C) inheritance that leads to a gain of function in  $3\beta$ HSD1, will have a sustained androgen synthesis from extragonadal precursor steroids and higher concentrations of DHT compared to wild-type *HSD3B1* (1245A) inheritance in the context of castration. Also, we expect intermediate levels of DHT in the heterozygous *HSD3B1* (1245C) group. We also hypothesize that Apalutamide will reverse the effects of elevated DHT on AR signaling in prostate tissue. For example, although DHT concentrations will be higher in the *HSD3B1* (1245C) groups, PSA expression will be equivalent among all groups. We anticipate that these studies will serve as the first step in identifying patients with prostate cancer who will benefit from upfront treatment with Apalutamide in addition to medical castration.

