## 2 Objectives

### 2.1 Primary Objective

To evaluate the differential effect of neo-adjuvant leuprolide and Apalutamide on dihydrotestosterone (DHT) concentration in benign prostate tissue based on *HSD3B1* genotype.

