## 6.2 Dosage and Administration

### 6.2.1 Description of Study agents and Administration

Study agents include Apalutamide and leuprolide. Apalutamide will be provided by the study. Subjects are to receive the following:

- Leuprolide 7.5 mg IM x 1 dose on day (-28)  $\pm$  3 days
- Apalutamide 240 mg (4 x 60 mg tablets) by mouth [PO] on a continuous once-daily dosing regimen.

Sufficient study medication for an entire treatment course till the day of surgery will be distributed on the first day of treatment. Apalutamide will be self-administered on an outpatient basis during the study, once daily, with or without food. Treatment will start on Day (-28)  $\pm$  3 days from the scheduled date for radical prostatectomy. Subjects may take Apalutamide up to and including the day before radical prostatectomy, at which time the medication will be discontinued.

It is anticipated that individual patients may occasionally forget to take a dose. In those cases, missed doses should only be replaced if the patient remembers within a 12-hour window. After that, patients should just take the next dose the following day, without compensating for the missed dose.

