### **Pharmacodynamics and Pharmacokinetics**

Onset of action: Following transient increase, testosterone suppression occurs in ~2-4 weeks of continued therapy.

Distribution: Males: Vd: 27 L

Protein binding: 43% to 49%

Metabolism: Major metabolite, pentapeptide (M-1)

Bioavailability: SubQ: 94%

Excretion: Urine (<5% as parent and major metabolite)

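### Does section 14.2 need a supporting analysis restricted to men whose serum testosterone is suppressed before surgery?

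*Combined protocol and SAP*

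**What the plan says.** The Protocol Summary predicts higher DHT in homozygous variant men than under wild-type "inheritance in the context of testosterone suppression". Section 1.7 says "inheritance in the context of castration". The primary objective in section 2.1 is worded differently: "To evaluate the differential effect of neo-adjuvant leuprolide and Apalutamide on dihydrotestosterone (DHT) concentration in benign prostate tissue", by genotype. It concerns the regimen as given and sets no suppression condition.

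Section 6.2.1 gives one 7.5 mg intramuscular leuprolide dose 28 days before scheduled surgery, plus or minus 3. The pharmacology text under 8.2 states: "Following transient increase, testosterone suppression occurs in ~2-4 weeks of continued therapy".

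The Study Calendar (section 11) schedules serum testosterone at baseline and before surgery; its footnotes allow collection 1 to 3 days before surgery or on the day. Tissue testosterone is a secondary endpoint. Section 1.3.1 cites two castrate levels, 1.7 nmol/L (historical) and 0.7 nmol/L (contemporary).

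The analysis text is one sentence in 14.2: "Differences between genotypes within and between tissue types will be analyzed using linear or non-linear models". The section also allows data transformation and plans correlations among hormones and markers.

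**The concern.** The hypothesis concerns DHT made from extragonadal precursors once the testes are switched off. Section 1.1 notes that "serum testosterone (T) is irreversibly converted to DHT in the prostate", so a man who still has testicular testosterone makes prostatic DHT without needing 3βHSD1 in the tissue. Such men would add DHT that has nothing to do with the genotype mechanism. That pulls the homozygous to wild-type ratio towards 1 and adds spread.

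The timing leaves room for this. Surgery on days 25 to 27 falls inside the quoted onset range of about 14 to 28 days. The 75% variability benchmark in 14.1 comes from men given 6 months of leuprolide, so it says little about suppression at four weeks.

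If the trend came out weak, two explanations would compete: no genotype effect, or incomplete suppression. Section 14.2 sets no rule for telling them apart. With two castrate levels in the protocol, a cut-off picked after seeing the data could be challenged.

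**Working it through.** **Inputs from 14.1.** 30 wild-type, 15 heterozygous and 12 homozygous men; two-sided 5% test; 4-fold difference with the heterozygous mean midway; SD of 125% of each genotype mean (75% in the alternative case).

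**Reproducing the plan's power.** Linear trend on allele count (0, 1, 2), normal data on the original scale, SD = CV × genotype mean, simulated:

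| Case | Stated in 14.1 | Recomputed |
|---|---|---|
| 4-fold, CV 125% | >80% | 79% |
| 4-fold, CV 75% | >95% | 99% |
| 3-fold, CV 75% | >90% | 96% |
| 2-fold, CV 75% | 75% | 77% |

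The model matches the plan to within about 2 points wherever 14.1 is close to its limit.

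**Assumptions, not in the protocol.** A share p of men is unsuppressed. Each of them has extra DHT of k times the wild-type mean, with k = 2, 4 or 8.

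**Dilution of the ratio.** For a true 4-fold effect the mean ratio becomes (4 + pk)/(1 + pk).
- p = 5%: 4.1/1.1 = 3.73, 4.2/1.2 = 3.50, 4.4/1.4 = 3.14.
- p = 1%: 4.02/1.02 = 3.94 (k = 2) down to 4.08/1.08 = 3.78 (k = 8).

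**Power at p = 5%, k from 2 to 8.** Log-scale SD = √ln(1 + CV²), which is 0.970 at CV 125% and 0.668 at CV 75%. On the original scale, the first range lets the SD grow with the extra DHT and the second does not.

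| Case | None unsuppressed | All men | Suppressed men only |
|---|---|---|---|
| Original scale, 4-fold, CV 125% | 79% | 56-75% or 70-79% | 77% |
| Original scale, 2-fold, CV 75% | 77% | 33-65% or 35-71% | 75% |
| Log scale, 4-fold, CV 125% | 99% | 97-99% | not tabulated; no room to gain |
| Log scale, 2-fold, CV 75% | 88% | 70-83% | 86% |

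**Other shares.**
- p = 1%: the original-scale design case gives 73-79% and the log-scale design case stays at 99%.
- p = 2%: log-scale 2-fold power is about 81-86%. The chance that none of 57 men is unsuppressed is 0.98^57 = 32%, and the restricted analysis would then be identical to the main one.
- p = 10%, in a variant where unsuppressed men sit at 4 or 10 times the wild-type mean whatever their genotype: the log-scale design case gives 95% or 90%, against 98% in the suppressed subset.

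**How far to trust the large losses.** The lowest figures come from untransformed normal data. At CV 125% that model puts Φ(−1/1.25) = 21% of values below zero. It is a poor guide to the effect of a few high outliers, which is the mechanism at issue. Section 14.2 allows transformation.

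**What restriction would cost.** At p = 5%, about 0.05 × 57 = 2.9 men leave, of whom 0.05 × 12 = 0.6 are homozygous. If there is no testicular contribution, dropping the top 5-10% by serum testosterone (assumed correlation with tissue DHT of 0 to 0.6) takes log-scale 2-fold power from 88% to 80-87%. In the original-scale design case with k = 2 and no SD growth, all men give 79% and suppressed men 77%, so restriction loses power.

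**The case for a change.** The best case for a change is that it is cheap and guards against an ambiguous null. Testosterone is already collected, a few sentences would do, and with homozygous men limiting accrual the study is hard to repeat. At 5% unsuppressed and k = 4, in the 2-fold case, the restricted test finds roughly half (46-55%) of the true effects that the all-men test misses; the reverse discordance is at most 3%. Under no genotype effect it rejects in 4.7-5.2% of trials, so it is not anti-conservative in these simulations.

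What stands is that 14.2 is silent and that a threshold fixed in advance is better than one chosen later. Three things weaken the rest.
- No passage says any man will be unsuppressed. Section 1.1 says androgen deprivation lowers testosterone below 1.7 nmol/L, the same cut-off the restriction would use, and 1.3 expects castrate levels. The onset line sits beside a description of a subcutaneous solution, whereas the trial injects intramuscularly, so it may not describe the product given.
- The material log-scale loss appears in the 2-fold case, which is not the design effect.
- Pre-operative testosterone is measured after treatment starts. Section 1.4 says 3βHSD "enzymatic activity is absolutely required for the synthesis of T and/or DHT", so the selection variable may itself depend on genotype. A restricted result that differed from the main one would have two readings of its own.

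**Conclusion.** No change is needed. The observation about 14.2 is correct, but it is a gap that analysts can fill sensibly. It leaves every stated number and rule in the plan intact. The comparison in all evaluable men answers the primary objective as worded, and the restricted analysis could only aid interpretation.

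The size depends entirely on two assumed quantities. With up to 5% unsuppressed, the design case loses at most about 2 points on the log scale (99% to 97%), and nothing visible at 1%. Larger losses need an unsuitable scale, a smaller true effect (log-scale 2-fold: 88% to 70-83% at 5%) or a higher share than the protocol suggests. If non-suppression were common, losses would exceed those tabulated at 5%, but the scheduled serum and tissue testosterone would make gross non-suppression visible. Counting men at or above 1.7 and 0.7 nmol/L by genotype is ordinary reporting that the present text allows, as is a restricted analysis labelled supportive.

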## 1.5 Preclinical Data

Recently, a gain of function single-nucleotide polymorphism (SNP) in *HSD3B1*(1245C; N367T) was identified that can also occur as a somatic mutation in CRPC tumors. Germline SNP variant of *HSD3B1*(1245C, rs1047303) occurs with a reported allele frequency of 22% in general population, but appears to vary widely by ethnicity. In a group of 118 prostate cancer patients at Cleveland Clinic, the frequency of the variant *HSD3B1*(1245C) allele is 36%. 3 $\beta$ -hydroxysteroid dehydrogenase isoenzyme-1 (3 $\beta$ HSD1), encoded by *HSD3B1*, is one of the three enzymes involved in converting DHEA from the adrenal gland to DHT in prostate cancer tissue. 3 $\beta$ HSD oxidizes 3 $\beta$ -hydroxyl to 3-keto and isomerizes  $\Delta^5$  to  $\Delta^4$  in the process of converting DHEA to AD. These reactions together make this step practically irreversible by an enzyme that is required for all possible pathways that lead to the synthesis of DHT. Chang et al have shown that CRPC sometimes expresses the 367T form of the *HSD3B1*, which increases metabolic flux from DHEA via the 5 $\alpha$ -dione pathway to DHT by protein resistance to ubiquitination and degradation rather than increased catalytic activity. This mutation increases protein half-life from 2.1 to 27 hours which leads to a profound accumulation of 3 $\beta$ HSD1 with subsequent increased flux to DHT and ultimately increased AR activation and prostate cancer progression. In addition, to study the possibility of *HSD3B1* (1245C) selection in human tumors, we sequenced matching germline and tumor DNA from 40 men with CRPC. Among these patients, the germline of 25, 11, and 4 individuals was homozygous wild type *HSD3B1* (1245A), heterozygous, and homozygous variant *HSD3B1* (1245C), respectively. Three of 25 (12%) CRPC tumors with homozygous *HSD3B1* (1245A) inheritance have acquired the *HSD3B1* (1245C) allele. Also, three of 11 (27%) CRPC tumors with heterozygous inheritance, have loss of heterozygosity (LOH) of the *HSD3B1* (1245A) allele, resulting in the *HSD3B1* (1245C) allele being predominantly detectable. In contrast, none of the 11 cases with heterozygous inheritance exhibited LOH of the *HSD3B1*(1245C) allele. These data support the role of the *HSD3B1* (1245C) allele in the development of CRPC. Moreover, our review of the clinical outcomes in 118 men with prostate cancer who were treated with ADT for biochemical failure after prostatectomy shows that inheritance of *HSD3B1*(1245C) allele that enhances the DHT synthesis may predict resistance to ADT in prostate cancer. In this group of patients allelic frequency of *HSD3B1* (1245C) was 36% with homozygous wild-type, heterozygous, and homozygous variant detected in 37%, 53%, and 10% of the patients. We demonstrated that median progression free survival (PFS), distant metastasis-free survival (DMFS), and overall survival (OS) diminished as a function of the number of variant alleles inherited, showing a gene-dosage effect and stepwise decrements with 0 vs. 1 vs. 2 variant alleles in all three endpoints.

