### 14.1 Sample Size and Accrual

In a recent report by Chang et al the prevalence of the homozygous *HSD3B1*(1245C) genotype was 10% in 40 CRPC patients. The prevalence however is to some extent race-dependent.

The prevalence of the wild type and heterozygous genotypes were approximately 2:1, and therefore the homozygous variant genotype is “rate-limiting” for accrual. The target enrollment is 12 patients who have the homozygous *HSD3B1*(1245C) genotype, 15 patients who are heterozygous, and 30 wild-type patients. Because of the low prevalence of homozygous *HSD3B1* (1245C), enrollment in each cohort will proceed until its target is reached. A subject who either prematurely discontinues from the study before completing 28 days of the treatment, prior to surgery, or for whom we are unable to obtain a tissue sample from, may be replaced in order to achieve target enrollment in each cohort. All safety and efficacy data from all accrued patients independent of the availability of post-treatment tumor material will be collected and analyzed.

Overall, based on the prevalence of the homozygous variant genotype, we predict that we may need to screen up to 120 patients to reach our accrual objective. Due to logistical restrictions, an accrual goal of 80 male patients may be needed in order to capture all objectives for a sample size of 57 patients. Accrual is expected to be approximately 2 years in the three cohorts.

With 57 patients there will be statistical power >80% to detect a 4-fold trend in the primary endpoint, DHT concentrations in the resected prostate tissue, as well as similar trends in other androgens and molecular markers. The calculation is based on a 2-sided test with 5% type I error; a codominance model where there is a 4-fold difference in hormone concentration between the wild-type and homozygous variant genotypes and a concentration approximately mid-way between the two for the heterozygous genotype; and that variability in this concentration could be as much as 125% of the mean hormone tissue concentration for each genotype. Note that 125% of the mean is a conservative estimate of variability. If it turns out in fact to be lower – e.g. similar to the 75% seen in a recent study in which patients were treated with 6 months leuprolide prior to RP, there will be >95% power to detect a 4-fold range, >90% to detect a 3-fold range, and 75% to detect a 2-fold range.

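### Section 14.2 plans hormone-marker correlations without genotype, so an unadjusted correlation alone cannot separate tracking from a shared genotype effect

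*Combined protocol and SAP*

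**What the plan says.** Section 14.2 gives the association analysis in one sentence: "Pearson or Spearman rank correlations will be used to assess associations between the concentrations of the different hormones and molecular markers". It adds that "All tests of statistical significance will be two-sided". It does not say whether genotype is adjusted for or stratified on, which scale is used (transformation is left open for the summaries), or whether benign and malignant tissue are kept apart. Genotype appears only in the separate sentence on models for differences between genotypes.

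Section 14.1 fixes the genotype mix by quota: "The target enrollment is 12 patients who have the homozygous *HSD3B1*(1245C) genotype, 15 patients who are heterozygous, and 30 wild-type patients", and "enrollment in each cohort will proceed until its target is reached". The power statement assumes "a 4-fold difference in hormone concentration between the wild-type and homozygous variant genotypes", with heterozygotes about mid-way and an SD of 125% of the mean, or alternatively 75%. It claims power for comparable trends in other androgens and in molecular markers. Section 3.1 likewise expects metabolite levels in heterozygotes to be intermediate.

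For PSA expression, however, the Protocol Summary and section 1.7 expect no genotype difference, because apalutamide should block the effect of the higher DHT. Section 10.5 calls the expression analyses exploratory.

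**The concern.** These correlations are the only analysis in section 14.2 that relates hormone levels directly to AR-regulated markers. The trial's idea is that apalutamide uncouples raised DHT from AR signalling. A positive DHT-marker correlation could be read as a sign that uncoupling failed.

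Genotype is expected to move DHT and the other androgens, and section 14.1 allows that it may move the markers. Two quantities that both rise from wild-type to homozygous variant will correlate over the whole sample, even if a man's DHT says nothing about his marker level once his genotype is known. With no genotype term, the reader of a significant correlation cannot tell which situation applies. Androgen-androgen pairs are the most exposed, since the plan expects the genotype trend in both members.

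**Working it through.** **Inputs from the documents.** Cohorts of 30/15/12 = 57; fold ranges of 4, 3 and 2; heterozygote mid-way; CV 125% or 75% (section 14.1). For the power statement, "The calculation is based on a 2-sided test with 5% type I error".

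**Assumptions not in the documents.** Log-normal data (a normal model is also tried); the same CV for markers as for hormones; 5% level for the correlations; one unadjusted correlation over all 57 men; within-genotype correlation zero, to isolate the genotype effect.

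**The plan's own figure.** Simulated regression on allele count (20,000 runs, normal errors, SD = CV × genotype mean) gives power of 79.7% for 4-fold at CV 125%. At CV 75% it gives 99.0%, 96.2% and 76.3% for 4-, 3- and 2-fold. The plan states >80%, >95%, >90% and 75%. The inputs therefore reproduce the stated power to within rounding.

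**Correlation induced by genotype, log scale.** With both quantities on the same trend, r = VB / (VB + s²), where VB is the between-genotype variance of the log means and s² = ln(1 + CV²).

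- 4-fold log means: 0, ln 2.5 = 0.916, ln 4 = 1.386.
- Mean = (15 × 0.916 + 12 × 1.386)/57 = 0.533. Mean square = (15 × 0.840 + 12 × 1.922)/57 = 0.626. VB = 0.626 − 0.533² = 0.341.
- CV 75%: s² = ln 1.5625 = 0.446, so r = 0.341/0.788 = 0.43.
- CV 125%: s² = ln 2.5625 = 0.941, so r = 0.341/1.282 = 0.27.

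For 4-fold with 2-fold (log means 0, 0.405, 0.693), the between-genotype covariance is 0.165 and the second variance is 0.081. Then r = 0.165/√(0.788 × 0.527) = 0.26 at CV 75%, and 0.165/√(1.282 × 1.022) = 0.14 at CV 125%. With n = 57 an observed |r| of about 0.26 is significant at 5%.

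Simulation (20,000 trials, zero within-genotype correlation, log scale):

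| Fold ranges | CV 75%: mean r, % significant | CV 125%: mean r, % significant |
|---|---|---|
| 4 and 4 | 0.44, 96% | 0.27, 54% |
| 3 and 3 | 0.32, 72% | 0.18, 28% |
| 4 and 2 | 0.26, 51% | 0.15, 19% |
| 4 and 1 (flat marker) | 0.00, 5% | 0.00, 5% |

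Spearman is similar (mean r 0.45 and 0.27 for 4 and 4). Placing the heterozygote at the geometric midpoint lowers the 4-and-4 figures to 92% and 47%.

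**Raw scale.** Under the normal model that reproduces the plan's power, 4 and 4 gives 66% (Pearson) and 58% (Spearman) at CV 75%, and 29% and 17% at CV 125%. These are lower, but still well above 5%.

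**Role of the quotas.** Section 1.5 reports "homozygous wild-type, heterozygous, and homozygous variant detected in 37%, 53%, and 10% of the patients", about 21/30/6 of 57. For that mix VB = (30 × 0.840 + 6 × 1.922)/57 − 0.628² = 0.250. So r = 0.250/0.696 = 0.36 (CV 75%) or 0.250/1.191 = 0.21 (CV 125%), against 0.43 and 0.27 with the quotas.

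**After adjustment.** Partial correlation given genotype has 57 − 2 − 2 = 53 degrees of freedom. On the log scale mean r returns to 0.00 and rejection to 5%. On raw values it does not: adjusted Pearson still rejects 12–15% with log-normal data and about 18% under the normal model, because the SD rises with the genotype mean. Adjusted ranks give about 5% with log-normal data and 6–8% under the normal model.

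**If genotype acts on the marker only through DHT** (DHT 4-fold, within-genotype r = 0.3, log scale), power falls from about 86% unadjusted to 61% adjusted at CV 75%, and from about 77% to 62% at CV 125%. Repeat runs differ by about a point. For a within-genotype r of 0.4 the adjusted test has 87% power.

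**The case against.** The strongest reply is that the protocol does not expect its lead marker to vary with genotype. If PSA is equivalent across groups, nothing is induced and the test keeps its 5% level. That stands: a reader might infer that the planned correlations will show spurious associations, but the documents support only that they can, where both quantities trend with genotype.

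Second, the hypothesised path runs from genotype through 3βHSD1 and DHT to AR signalling. If genotype moves a marker only through DHT, the between-genotype part of the correlation is real tracking. A reader might therefore go too far in inferring that an unadjusted correlation cannot show that DHT tracks a marker. It can reflect tracking; it cannot, alone, tell tracking from shared genotype.

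Third, blaming the genotype quotas is tempting. They amplify the effect, but the natural mix produces most of it.

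Fourth, section 14.2 never says that the genotypes are pooled. That is also true: the unadjusted whole-sample correlation is the natural reading of a sentence with no qualifier, and the gap is one of specification.

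Finally, no listed objective asks whether hormones track markers within genotype, and the expression work is exploratory. This limits the severity but does not remove the ambiguity.

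**Conclusion.** The point holds as a minor one. Section 14.2 takes no account of genotype in its correlations, although the sample is filled by genotype and the plan expects or contemplates genotype trends in the quantities to be correlated. With a 4-fold range in both and no within-genotype association, an unadjusted log-scale correlation is significant in 54–96% of trials. With 4-fold and 2-fold it is 19–51%, and with one quantity flat it is 5%. The size depends on the shared trend, the CV and the scale, and on the assumptions that markers are as variable as hormones and that the 5% level applies.

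The conclusion is confined to what an unadjusted correlation can be taken to mean. It does not reach the primary comparison of DHT between genotypes, which is unaffected.

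**What to change.** In section 14.2, pre-specify genotype-adjusted (partial) Pearson correlations on log values, or partial correlations on ranks, with genotype as a three-level factor and benign and malignant tissue analysed separately. Report them beside the unadjusted correlations, and base any claim of association beyond shared genotype on the adjusted value. The scale must be named, because adjusting raw values does not restore the 5% level.

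This needs about one sentence, two degrees of freedom and no further patients or samples. It is not entirely free: if genotype acts on the marker only through DHT, the adjusted test loses the power shown above, which is why both values should be shown. Fully separate correlations in each genotype are a poor substitute, since 80% power would need r of 0.49, 0.67 and 0.73 with 30, 15 and 12 men.
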